4.1.3.3 Randomization

Eligible patients are randomized in a double-blinded fashion at Week 26 at a 1:1 ratio either to continue treatment with LCI699 at the same dose or to matching placebo. Patients are stratified at randomization according to: LCI699 dose at Week 24 ($\leq 5\text{mg b.i.d.}$ vs. $> 5\text{mg-b.i.d.}$); and history of pituitary irradiation (yes/no).

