6.5.2 Treatment assignment or randomization

At week 26, and based upon the mUFC results from the Week 24 assessment, and the LCI699 dose at week 26 compared to week 12, patients will either:

- Not be randomized, and continue LCI699 treatment according to the schedule in [Table 7-3](#).
- Be randomized to one of the two treatment assignments (LCI699 or placebo) in a 1:1 ratio ([Section 4.1](#) and [Section 6.1](#)).

Randomization will be stratified by LCI699 dose at Week 24 ($\leq 5\text{mg b.i.d.}$ vs. $> 5\text{mg b.i.d.}$); and history of pituitary irradiation (yes/no).

The randomization numbers will be generated using the following procedure to ensure that treatment assignment is unbiased and concealed from patients and investigator staff. A patient randomization list will be produced by the Interactive Response Technology (IRT) provider using a validated system that automates the random assignment of patient numbers to randomization numbers. These randomization numbers are linked to the different treatment arms, which in turn are linked to medication numbers. A separate medication randomization list will be produced by or under the responsibility of Novartis Global Clinical Supply using a validated system that automates the random assignment of medication numbers to medication packs containing each of the study treatments.

Prior to dosing on Week 26, all patients who fulfill mUFC criteria will be randomized via IRT to one of the treatment arms. The investigator or his/her delegate will call or log on to the IRT and confirm that the patient fulfills mUFC criteria. The IRT will assign a randomization number to the patient, which will be used to link the patient to a treatment arm and will specify a unique medication number for the first package of study treatment to be dispensed to the patient. The randomization number will not be communicated to the caller.

The randomization scheme for patients will be reviewed and approved by a member of the Biostatistics Quality Assurance Group. Specific instructions for IRT will be provided separately to each study site.

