10.5.2 Other secondary efficacy objectives

10.5.2.1 Compare the time-to-last control of mUFC during the randomized withdrawal period between patients randomized to continued LCI699 and placebo

Time-to-last control of mUFC during the randomized withdrawal period will be analyzed using K-M plot and stratified logrank test. Time-to-last control of mUFC is defined as the time (in days) from randomization to the time of the last normal UFC assessment ($mUFC \leq ULN$ based on central laboratory result) before early discontinuation or completion of randomized withdrawal period, whichever is earlier. RAS will be used for this analysis.

10.5.2.2 Assess the complete, partial, and overall response rate at Week 12, Week 24, Week 48, and during the extension period

Proportion of complete responder (enrolled patients with $mUFC \leq ULN$), partial responder (enrolled patients with $mUFC > ULN$ and at least 50% reduction from baseline), and overall responder (enrolled patients with $mUFC \leq ULN$ or have at least 50% reduction from baseline) at Week 12 (end of period 1), Week 24 (end of period 2) and Week 48 (end of period 4) as well as at scheduled time points during the extension period (provided adequate follow-up as specified in the SAP) and the last available assessment will be summarized using point estimates and 95% CIs.

10.5.2.3 Assess the change in mUFC during the core and extension period of the study

For the actual and percentage change in mUFC from baseline, descriptive summaries will be provided for every visit in core and extension (provided adequate follow-up as specified in the SAP) at which UFC is collected. 95% CIs for the percentage change from baseline will also be provided.

For the actual and percentage change in mUFC from the randomization (Week 26) to the end of randomized withdrawal period, or the last mUFC measurement prior to early discontinuation, whichever occurs earlier, in addition to the descriptive summaries, the difference between two randomized arm and associated 95% C.I. will be estimated with adjustment for mUFC at randomization. RAS will be used for the analysis.

10.5.2.4 Assess the change in cardiovascular-related metabolic parameters associated with Cushing's disease during the core and extension period of the study

For cardiovascular-related metabolic parameters associated with Cushing's disease (e.g. fasting glucose, HbA1c, fasting lipid profile, SBP, DBP, weight, waist circumference and BMI):

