For actual and percentage change from baseline during the core and extension period (provided adequate follow-up as specified in the SAP) of the study, descriptive summaries will be provided.

For the actual and percentage change from the randomization (Week 26) to the end of randomized withdrawal period, or the last measurement available prior to early discontinuation, whichever occurs earlier, in addition to the descriptive summary, the difference between two randomized arm and associated 95% C.I. will be estimated with adjustment for corresponding parameter value at randomization. RAS will be used for the analysis.

10.5.2.5 Assess the change from baseline in physical features of Cushing's disease by photography

For each of physical features of Cushing's disease: facial rubor, hirsutism, striae, supraclavicular fat pad, dorsal fat pad, proximal muscle wasting (atrophy), central (abdominal) obesity, and ecchymoses (bruises). The change from baseline at Week 12, 24, 34 and 48 as well as during the extension at Week 72 and EOT extension will be assessed using shift table.

10.5.2.6 Assess the change from baseline in bone mineral density by DXA scan at Week 48 and the last available assessment

For bone mineral density measured by DXA scan at the lumbar spine and total hip, descriptive summaries of actual and percentage change from baseline at Week 48 and the last available assessment will be provided.

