10.5.7 Patient-reported outcomes

The CushingsQoL score is identified as the primary PRO variable of interest. EQ-5D utility index and visual analogue scale (VAS) scores, and Beck Depression Inventory-II (BDI) total score are identified as secondary PRO variables of interest. The FAS will be used for analyzing PRO data. No multiplicity adjustment will be applied.

[figure not shown]
Change from Week 24 in the CushingsQoL score during Study Period 3 will be analyzed using a linear mixed effect model for longitudinal data to assess the treatment effect over time including terms for treatment, stratification factors, time of visit (in weeks counting from the time of randomization to the time of a particular post baseline measurement), treatment by time of visit interaction, and Week 24 score. The differences in least square means between LCI699 and placebo group, and the corresponding 2-sided 95% confidence interval (CI) at each timepoint will be presented. Descriptive statistics will be used to summarize the raw and absolute change from baseline for the scores at each scheduled assessment during the core and extension periods (Week 72, 96, and EOT extension) of the study.

[figure not shown]
Similar analyses will be performed for EQ-5D utility index and visual analogue scale (VAS) scores, and Beck Depression Inventory-II (BDI) total score.

Missing items data in a scale will be handled based on each instrument manual. Additional details for handling missing items data will be specified in the analysis plan for instruments with no missing data handling criteria in the instrument manual.

No imputation will be applied if the total scores are missing at a visit. Patients with Week 26 and at least one non-missing post-Week 24 assessments during the Study Period 3 will be included in the linear mixed effect model analysis. All available data until completion or early discontinuation during Period 3 will be used in the linear mixed effect models analyses which assume that the missing scores at any time point are missing-at-random. Additional sensitivity analysis may be performed to assess the possible violation of missing-at-random assumption for the missing data mechanism if deemed appropriate. Details will be specified in the SAP.

[REDACTED]

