2.7 Analysis of secondary efficacy objectives

For the objectives identified below, the definition of Baseline/Randomization assessment and the method of computing confidence intervals are specified in Section [2.1.1.2](#) and Section [2.1.1.8](#) respectively. Last observation carried forward (LOCF) method will not be used in any of these analyses. For analysis using FAS, results will be presented by LCI699 group, Placebo group, Non-randomized patients, and All patients.

2.7.1 Compare the time-to-last control of mUFC during the randomized withdrawal period between patients randomized to continued LCI699 and placebo

The results of this objective were reported in the interim CSR, and will not be repeated for the Final CSR.

2.7.2 Assess the complete, partial, and overall response rate at Week 12, Week 24, Week 48, and during the extension period

The proportion of complete responders (enrolled patients with $mUFC \leq ULN$), partial responders (enrolled patients with $mUFC > ULN$ and at least 50% reduction from baseline), and overall responders (enrolled patients with $mUFC \leq ULN$ or have at least 50% reduction from baseline) will be summarized using point estimates for every scheduled visit in the core and extension (provided [adequate follow-up](#)) at which UFC is collected. 95% 2-sided CIs for response rates will be provided for Week 48, Week 60, Week 72 and the last available assessment of the study. The FAS will be used for the analyses.

2.7.3 Assess the change in mUFC during the core and extension period of study

For the actual value and change in mUFC from baseline during the overall study period, descriptive summaries will be provided for every scheduled visit in the core and extension (provided [adequate follow-up](#)) at which UFC is collected. The FAS will be used for the analysis.

Patients randomized to placebo during the RW period, will not have their mUFC values included in the analysis for visits at which they received placebo.

2.7.4 Assess the change in cardiovascular-related metabolic parameters associated with Cushing's disease during the core and extension period of the study

The following parameters will be analyzed: glucose, HbA1c, fasting lipid profile, SBP, DBP, weight, waist circumference and BMI).

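### The randomized comparisons of Week 26–34 change in mUFC and cardiometabolic parameters name no stratification factor, so their confidence intervals may be conservative

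*Protocol*

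**What the plan says.** Protocol 4.1.3.3 fixes the design: "Patients are stratified at randomization according to: LCI699 dose at Week 24", in two groups split at 5 mg b.i.d., and by history of pituitary irradiation. Protocol 6.5.2 repeats this: "Randomization will be stratified by LCI699 dose at Week 24" and irradiation history. Allocation is 1:1.

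The strata then appear in three randomized analyses:

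- the primary Cochran–Mantel–Haenszel test (Protocol 10.4.2);
- the logrank test for time-to-last control (10.5.2.1);
- the mixed model for patient-reported outcomes in Study Period 3 (10.5.7), "including terms for treatment, stratification factors, time of visit".

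They do not appear in two others:

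- For mUFC change from randomization (10.5.2.3), "the difference between two randomized arm and associated 95% C.I. will be estimated with adjustment for mUFC at randomization".
- For glucose, HbA1c, lipids, blood pressure, weight, waist and BMI (10.5.2.4), the difference "will be estimated with adjustment for corresponding parameter value at randomization".

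The supplied SAP covers the Final CSR. Its 2.7.3 and 2.7.4 plan descriptive summaries only, with no comparison of the randomized arms over Weeks 26–34. Its Introduction refers the core-phase analyses to a separate SAP with cover date 06-Jul-2018.

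**The concern.** When allocation is balanced within strata, the arm difference is already protected from chance imbalance in those strata. A model that omits them still counts the variation between strata as error. If the strata predict the outcome, the model-based standard error is then larger than the true sampling error. The interval is wider than it has to be, and coverage exceeds 95%.

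These are the protocol's randomized, blinded estimates of the effect on cortisol level and on cardiometabolic parameters, with about 33 patients per arm, so precision is scarce. The protocol gives no reason for treating these two comparisons differently from the other three.

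**Working it through.** **Inputs from the documents**

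- Planned size: 33 per arm, so N = 66 (Protocol 10.8). This agrees with 132 enrolled × 50% eligible = 66.
- Expected strata shares: 10%, 40%, 10%, 40% (Protocol 10.8).
- Covariate named: the value at randomization. SAP 2.1.1.2 takes this as the last value within 21 days before the first randomized dose.

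**Assumptions, not in the documents**

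- A linear model with arm and the value at randomization.
- R² is the share of variance in the change that the two strata explain after that value is in the model. The documents give no figure, so a range including zero is used.

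**Step 1: the plan's own figure.** The plan states no power, SD or interval width for these comparisons. The nearest figure is 87% power for the primary test at 70% versus 30%. The two-proportion formula with continuity correction gives 33 per arm for 87% power (28 without the correction). Simulating the stratified test with four strata near 10/40/10/40 gives 86.8% with the correction and 91.4% without (200,000 runs). The 87% therefore reproduces, and N = 66 is a sound basis.

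**Step 2: interval width by formula.** Without the strata the error degrees of freedom are 66 - 3 = 63. With two main effects they are 66 - 5 = 61. The ratio of half-widths, with strata to without, is

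ratio = √(1 - R²) × t(0.975, 61) / t(0.975, 63), where the t-ratio is 1.0006.

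- R² = 0: 1.0000 × 1.0006 = 1.001
- R² = 0.05: 0.9747 × 1.0006 = 0.975
- R² = 0.10: 0.9487 × 1.0006 = 0.949
- R² = 0.20: 0.8944 × 1.0006 = 0.895

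Fitting all four strata cells (60 degrees of freedom) changes these by less than 0.001.

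**Step 3: coverage by simulation.** Settings: N = 66, strata as above, permuted blocks of 4 within strata (block size assumed), R² split equally between the two factors, 20,000 runs per value.

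| Assumed R² | Mean width change from adding strata | Coverage without strata | Coverage with strata |
|---|---|---|---|
| 0 | +0.2% | 95.0% | 95.0% |
| 0.05 | -2.5% | 95.5% | 95.0% |
| 0.10 | -5.2% | 95.9% | 94.8% |
| 0.20 | -10.8% | 97.1% | 95.1% |

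The Monte Carlo standard error of a coverage near 95% is √(0.95 × 0.05 / 20,000) = 0.15 percentage points.

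Formula and simulation agree. The omission costs nothing if the strata are uninformative, and the cost grows with R². Adding the strata when they predict nothing widens the interval by 0.1% to 0.2%.

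**The case against.** **The case against**

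- The protocol names one covariate without excluding others, and the core-phase SAP may give the full model. This stands. The point concerns the protocol text and must be checked against that SAP.
- No document shows that the strata predict the Week 26–34 change. Protocol 2.3 reports no apparent relation between dose and baseline mUFC in the proof-of-concept study, and 2.6 calls the confounding effect of radiation low. Neither statement concerns change after withdrawal, so they do not settle R². They do rule out asserting that the intervals are too wide.
- Intervals without the strata remain valid, since their coverage is at or above 95%. These are other secondary estimates with no alpha assigned. Both stand and limit the importance of the point.

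**Stronger readings that the documents do not support**

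- A reader might infer that using the last value before early discontinuation contradicts SAP 2.7: "Last observation carried forward (LOCF) method will not be used in any of these analyses". That sentence governs the Final CSR analyses in SAP 2.7, which do not include this comparison. The last value before discontinuation is the prespecified endpoint (Protocol Table 3-1, repeated in SAP Table 1-1).
- A reader might infer that only placebo patients are cut short. The exit rule in Protocol 4.1.3.6 applies to both arms. The planning rates, 30% and 70% response, imply more placebo exits, but not that every placebo patient exits or that every LCI699 patient reaches Week 34.
- A reader might want to put a size on the resulting bias in mUFC. That needs the rebound speed and the variances, which the documents do not give. Simulating the exit rule with an untreated median of 2–4 × ULN, log SDs of 0.6 between and 0.3 within patients, and rebound half-times of 0.25–4 weeks (all assumed) put the last placebo value anywhere from 8% above to 39% below the Week 34 level. Even the sign is not fixed.

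**Conclusion.** The inconsistency is real. Protocol 10.5.2.3 and 10.5.2.4 name no stratification factor, although randomization and the other three randomized analyses use both. The precision loss is conditional. At N = 66 the intervals could be about 2.5% narrower if the strata explain 5% of the residual variance, 5% narrower at 10%, and 10.5% narrower at 20%. At zero there is no gain. The error, if any, is on the conservative side.

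A reader might infer that the reported intervals are in fact too wide. The documents support only that they may be, because they give no R² and the core-phase SAP is not one of the two documents. The primary and key secondary conclusions and the sample size do not change.

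**What to change.** Add Week 24 dose group and history of pituitary irradiation as covariates to the models in Protocol 10.5.2.3 and 10.5.2.4. If the core-phase SAP of 06-Jul-2018 already does so, cite it instead.

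The study was unblinded at the core database lock on 10-May-2018 (SAP 1.2.3) and core results have been reported, so any re-analysis should be labelled supplementary. The cost is one model line per endpoint and one table. No new data are needed, and the loss in width is at most about 0.2% if the strata are not prognostic.

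Optionally, for mUFC, add a supplementary repeated-measures model over the scheduled visits at Weeks 26 to 34 with the same covariates. Missing-at-random is plausible there, because exit for loss of control is triggered by observed mUFC. State that this model targets a different estimand, the outcome had patients stayed on randomized treatment. The argument does not carry over directly to the cardiometabolic parameters, because their own values do not trigger exit.

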10.5.2.7 Assess the time-to-escape under treatment of LCI699

Escape is defined as the first loss of control of UFC that meets all of the following criteria:

- prior normalization of mUFC has occurred ($mUFC \leq ULN$)
- both the mean UFC and at least 2 individual values contributing to that mUFC have to be $>1.5 \times ULN$
- the loss of control of UFC is not related to a dose interruption or dose reduction due to safety reasons
- happens beyond 12-week dose titration period (Study Period 1).

For patients who attained normal mUFC (\leq ULN), time-to-escape will be analyzed using K-M plot. Time-to-escape is defined as the time (in days) between the first UFC assessment with $mUFC \leq ULN$ and either the UFC assessment of escape (event) or last UFC assessment before discontinuation of LCI699 treatment (censored), whichever occurs earlier.

Patients randomized to placebo are not included in this analysis.

10.5.3 Safety objectives

10.5.3.1 Analysis set and grouping for the analyses

Analysis set and treatment groups (see [Section 10.1](#) and [Section 10.3](#)) used for safety analyses will be described below:

- For study period up to Week 26: SAS by All patients only.
- For randomized withdrawal period: SASR by LCI699 group and Placebo group
- For overall study period while on LCI699: SAS by LCI699 group, Placebo group, Non-randomized patients, and all patients.
- In addition to the above mentioned analysis, other post-treatment safety data collected will be included in listings and flagged as appropriate.

The overall observation period will be divided into three mutually exclusive segments:

1. pre-treatment period: from day of patient's informed consent to the day before first dose of study medication
2. on treatment period: from day of first dose of study medication to 30 days after last dose of study medication
3. post-treatment period: starting at day 31 after last dose of study medication

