4.1.3.6 Discontinuation from randomized withdrawal

During the randomized withdrawal study period, the patient must be discontinued from the randomized withdrawal period, declared a non-responder, if the mUFC increases to $> 1.5 \times$ ULN, and at least 2 individual urine samples show UFC $> 1.5 \times$ ULN at a single visit (scheduled or unscheduled).

After discontinuation from randomized withdrawal, or at the end of the randomized withdrawal period (Week 34), whichever comes first, the patient resumes open-label LCI699 at a dose selected by the investigator.

Patients who are discontinued from the study for reasons other than those described above during the randomized withdrawal period are no longer in the study, and consequently they are not permitted to receive open-label LCI699 and cannot move forward to Study Period 4.

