10.5.3.2 Adverse events (AEs)

Summary tables for adverse events (AEs) will include only AEs that started or worsened during the on-treatment period, the **treatment-emergent** AEs. However, all safety data (including those from the pre and post-treatment periods) will be listed and those collected during the pre-treatment and post-treatment period are to be flagged. The incidence of treatment-emergent adverse events (new or worsening from baseline) will be summarized by system organ class and or preferred term, severity (based on CTCAE version 4.03 grades), type of adverse event, relation to study treatment.

Serious adverse events, non-serious adverse events and adverse events of special interest (AESI) during the on-treatment period will be tabulated.

All deaths will be listed.

All AEs, deaths and serious adverse events (including those from the pre and post-treatment periods) will be listed and those collected during the pre-treatment and post-treatment period will be flagged.

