10.8 Sample size calculation

Eligible patients will be stratified at randomization according to: LCI699 dose at Week 24 ($\leq 5\text{mg bid}$ vs. $> 5\text{mg bid}$); and history of pituitary irradiation (yes/no). It is estimated that 10 %, 40%, 10% and 40 % of randomized patients respectively will be in the 4 strata defined by two randomization stratification factors ($\leq 5\text{mg b.i.d}$ and Yes; $\leq 5\text{mg b.i.d}$ and No; $> 5\text{mg b.i.d.}$ and Yes; and $> 5\text{mg b.i.d.}$ and No) based on the following considerations:

1. LCI699 dose at week 24 ($\leq 5\text{mg b.i.d.}$ vs. $> 5\text{mg b.i.d.}$): Based on the data from the PoC study, 5mg b.i.d. is estimated to be the median LCI dose at week 24 for this phase 3 trial.
2. History of pituitary irradiation (Yes/No): Although supportive data is not available, it is assumed that approximately 20% of randomized patients will have a history of pituitary radiation.
3. In the absence of data to expect otherwise, it is assumed that these two stratification factors are independent of each other.

To detect a difference of 40% in complete response rate between 70% in LCI699 arm and 30% in placebo arm (equivalent odds ratio equals 5.444), a sample size of 33 patients per arm will be considered adequate based on a two-sided Cochran-Mantel-Haenszel (CMH) test at the 0.05 level with 87% power. Assuming that $\geq 50\%$ of enrolled patients will be eligible for randomization (mUFC \leq ULN at the end of the 24 week open-label LCI699 study period), 132 patients need to be enrolled into the study.

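### Adverse events in the randomized withdrawal period are planned as crude percentages by arm, with no stated end to the at-risk window, although the exit rule is expected to shorten exposure mainly on placebo

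*Protocol*

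**What the plan says.** **Comparison.** Protocol 10.5.3.1 gives the analysis set and grouping: "For randomized withdrawal period: SASR by LCI699 group and Placebo group". Section 10.5.3.2 gives the measure: "The incidence of treatment-emergent adverse events (new or worsening from baseline) will be summarized by system organ class". Neither section has a person-time denominator, a time-to-first-event analysis or a window specific to this period. The one on-treatment definition, in 10.5.3.1, covers the whole study and runs to 30 days after the last study medication. Exposure duration is summarized descriptively (Protocol 10.3) but is not linked to the event tables.

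**Exit rule.** Protocol 4.1.3.6 says that "the patient must be discontinued from the randomized withdrawal period, declared a non-responder" once mUFC and at least two individual samples exceed 1.5 x ULN. The patient then resumes open-label LCI699. Section 4.1.3.7 expects such exits typically before Week 34, and 4.1.3.4 schedules mUFC every 2 weeks.

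**Planned response.** Protocol 10.8: "To detect a difference of 40% in complete response rate between 70% in LCI699 arm and 30% in placebo arm".

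**SAP.** The supplied SAP covers the Final CSR only. Its section 1 refers the core-phase analyses to a separate SAP with cover date 06-Jul-2018. Sections 2.8 and 2.8.1.3 leave events that start on placebo out of the summaries, so this document neither makes the randomized comparison nor corrects it.

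**The concern.** The 8-week randomized withdrawal period is the trial's only placebo-controlled source of safety data. Protocol 8.7 itself notes that nearly all other safety data are open-label. A crude percentage depends on how long each patient is observed, and here the observation time depends on the efficacy outcome.

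Two readings of the window are possible, and they lead to different problems:

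- **Window closes at exit.** Placebo patients have less time in which to report an event. Their percentage falls even if the weekly hazard is the same in both arms.
- **Window stays open to Week 34.** Observation time is equal, but events after LCI699 is restarted are counted under placebo. Protocol 4.1.3.7 warns of unstable cortisol and glucocorticoid withdrawal at that point.

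These are alternatives and cannot both apply. A reader of the protocol cannot tell from 10.5.3 which one governs, and so cannot tell how to read a difference between arms.

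**Working it through.** **Inputs from the documents.** Allocation is 1:1 (Protocol 4.1.3.3). Protocol 10.8 states that "a sample size of 33 patients per arm will be considered adequate". The power it claims is 87%, with two-sided alpha 0.05. The period lasts 8 weeks with visits every 2 weeks. Planned non-response is 70% on placebo and 30% on LCI699.

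**The plan's own figure.** The continuity-corrected two-proportion formula reproduces it. Without correction, n = [1.960 x sqrt(2 x 0.5 x 0.5) + 1.126 x sqrt(0.7 x 0.3 + 0.3 x 0.7)]² / 0.4² = 28.0. With correction, n = (28.0/4) x [1 + sqrt(1 + 4/(28.0 x 0.4))]² = 32.8, so 33 per arm. The documents give no figure for adverse event risk, exit rate or exit time.

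**Model (assumed).** Constant hazard λ, equal in both arms, with λ = -ln(1 - R)/8 for an assumed 8-week risk R. If a share p(t) leaves at week t and the window closes there, crude incidence = Σ p(t) x [1 - exp(-λt)].

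**Base scenario.** R = 50%, so λ = 0.0866 per week. Exits come one week after the Week 28, 30 and 32 visits, at t = 3, 5 and 7. The event probabilities at 3, 5, 7 and 8 weeks are 0.229, 0.352, 0.455 and 0.500.

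- Placebo, exits 25%, 20% and 15%: 0.25 x 0.229 + 0.20 x 0.352 + 0.15 x 0.455 + 0.40 x 0.500 = 39.6%. Mean exposure is 6.0 weeks.
- LCI699, exits 10% in the same 25:20:15 split: 48.3%. Mean exposure is 7.7 weeks.
- Ratio 1.22; difference 8.7 points.

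**Sensitivity.** With that split and 10% exits on LCI699, R from 30% to 60% and placebo exits from 40% to 65% give ratios of 1.11 to 1.28. Other scenarios, all at R = 50%:

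| Exits, placebo / LCI699 | Exit weeks | Crude incidence, placebo / LCI699 | Ratio |
|---|---|---|---|
| 60% / 26% (86% of planned non-responders in each arm) | 3, 5, 7 | 39.6% / 45.5% | 1.15 |
| 35% / 15% (half of non-responders in each arm) | 3, 5, 7 | 43.9% / 47.4% | 1.08 |
| 70% / 30% (all non-responders) | 2, 4, 6 evenly | 35.0% / 43.6% | 1.24 |
| 35% / 15% | 2, 4, 6 evenly | 42.5% / 46.8% | 1.10 |

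In the third row, a 2-week delay from sample to exit gives 43.0% against 47.0%. A 30-day tail after each patient's exit or Week 34 gives 55.2% against 61.1%. A fixed 8-week window for everyone gives no gap under equal hazards, but counts resumed LCI699 under placebo.

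**Check of the remedy.** Also in the third row, first events divided by patient-weeks up to the first event or exit give 8.66 per 100 patient-weeks in both arms, a ratio of 1.00.

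**The case against.** **The governing plan may be elsewhere.** Randomized-withdrawal safety is core-phase data, and the core-phase SAP was not supplied. This stands: the point can be made about Protocol 10.5.3, not about everything the sponsor planned.

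**The direction is not fixed.** A reader might infer that the analysis is biased against LCI699 in any case. The documents do not support that. It follows only if the window closes at exit, or at exit plus 30 days.

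**The open-window reading fits the text poorly.** Protocol 2.2 and 4.1.3.6 treat exit as leaving the period, the visit schedule has a separate end visit for it, and the supplied SAP separates time on placebo by date (2.4.1, 2.8.1.3). Closure at exit is therefore the more natural reading. What remains is that 10.5.3 does not state the boundary.

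**Non-response is not exit.** Non-responders also include patients between 1 and 1.5 x ULN, those with a missing Week 34 value (10.4.3), and those first over the limit at Week 34, who lose no exposure. No passage supports a larger early-exit share of non-responders on placebo than on LCI699. Equal shares in the base scenario's exit pattern give about 1.08 to 1.15, so the base 1.22 depends on an assumed asymmetry.

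**The consequence is limited.** No test, margin or decision rule is attached to these tables. With 33 per arm, the base gap of 8.7 points compares with a standard error of sqrt[(0.396 x 0.604 + 0.483 x 0.517)/33], about 12 points. Exposure is already to be described, so an attentive reader could see the imbalance. This limits the weight of the point but does not remove it.

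**A rate is not a full cure.** It removes the artefact fully only if hazards are roughly constant, and it does not correct for exit driven by mUFC. Both limits stand and should be stated with the result.

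**Conclusion.** The concern holds in a limited form. The protocol plans crude incidence by arm, leaves the end of the randomized-period window unstated, and has an exit rule expected to shorten placebo exposure.

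If the window closes at exit and hazards are equal and constant, LCI699 would look modestly worse, by an illustrative risk ratio of about 1.1 to 1.3. That range rests on assumed exit fractions, exit times and event risk, and is not a forecast. Larger ratios can be produced: 70% against 10% exits at Weeks 2, 4 and 6 gives 1.37. They need strongly unequal exit shares that the documents do not support. Events clustered in the first two weeks would shrink the gap.

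A reader might go further and infer an inflated type I error or a controlled safety comparison that cannot be used. Neither follows. The tables are descriptive, and the gap is a risk of misreading that a small addition would largely remove. The core-phase SAP may already contain that addition.

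**What to change.** For the randomized withdrawal period, in Protocol 10.5.3.1 and 10.5.3.2 or the matching core-phase SAP section:

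1. Define the at-risk window as the first randomized dose to the earlier of the last randomized dose or the day before the first open-label LCI699 dose.
2. Show exposure to randomized drug by arm alongside the event tables.
3. Beside the crude percentages, give the exposure-adjusted incidence by arm: patients with a first event per patient-week on randomized drug, with the difference and 95% CI. Count patient-weeks only up to the first event. In the 70%/30% scenario, using full exposure instead gives 43.6/6.8 = 6.41 against 35.0/5.2 = 6.73 per 100 patient-weeks, which is not equal.
4. Label the result supplementary, since the core phase was unblinded on 10-May-2018 (SAP 1.2.3). Note that it assumes a roughly constant hazard and does not correct for mUFC-driven exit.

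If the SAP of 06-Jul-2018 already does this, a cross-reference is enough.

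**Cost.** No new data collection: SAP 2.4.1 already uses the duration of exposure to placebo. It needs a little programming and one more column in the randomized-period tables.
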